12.2.2 Safety variables

As noted earlier, safety endpoints will include:

- Symptoms
- Findings on physical examination including vital signs
- Routine clinical testing daily including
 - Complete blood counts
 - Metabolic and liver panels
 - Coagulation panel (platelets, prothrombin time and partial thromboplastin time)
- Unexpected adverse events

These will be subjected to descriptive analyses and differences between the treatment groups analyzed for significance as described below.

12.3 Statistical Methods

All tests for significance will be two sided at the 5% significance level and accordingly 95% confidence intervals will be determined.

The main clinical efficacy variable, the occurrence or nonoccurrence of an acute attack each of the 4 weeks following test infusion, will be analyzed by logistic regression with treatment as a factor and drug dose as a covariate. Data for any post randomization exclusions will be listed and the possible impact assessed.

Use of Panhematin[™] and opioids for treatment of porphyria symptoms during the 4 weeks following treatment will be analyzed by exact two sample Wilcoxon tests or by Fisher's exact test.

Supplementary analyses of the role of demographic and clinical features will be performed.

Adverse events will be coded and analyzed descriptively.

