- To evaluate in 20 patients who are on a Panhematin[™] prophylactic regimen whether a blinded dose of Panhematin[™] is more effective than placebo in preventing an attack within the next 1-4 weeks.
- To evaluate in these 20 patients whether hemin is as safe and well tolerated as placebo when administered in a blinded fashion. Safety parameters will include the frequency and severity of phlebitis, nausea, vomiting and coagulation abnormalities.

Secondary Objectives:

• To evaluate the biochemical effects of Panhematin[™] in patients treated with Panhematin[™] to prevent attacks of acute porphyria by measuring urinary 5-aminolevulinic acid and porphobilinogen and serum porphobilinogen. This will determine whether biochemical measurements are predictive of efficacy in preventing an attack.

Exploratory Objectives:

- To evaluate effects of clinical features, such as sex, age and the factors that precipitate attacks of porphyria on response to preventive administration of Panhematin[™].
- To evaluate effects of genetic features, including the nature or the *PBGD*, *CPOX* or *PPOX* mutation on response to preventive Panhematin[™]
- To evaluate the use of Panhematin™ reconstituted with 25% human albumin in patients treated to prevent acute attacks of porphyria

Porphyria Laboratory and Center Date: June 18, 2019 IND 13,929

2.1 Endpoints.

The primary efficacy endpoint is whether a Panhematin[™] is more successful than placebo in preventing a porphyria attack within the next 1-4 weeks when given as the patient's usual periodic prophylactic regimen given within approximately one week. Symptoms during past acute attacks should have included severe abdominal pain requiring a narcotic analgesic. An acute porphyric attack is defined by the presence of abdominal pain and one or more other characteristic manifestations such as tachycardia (heart rate 100 per minute or greater), nausea, vomiting, constipation, extremity pain, acute hypertension, low-grade fever, objective evidence of peripheral neuropathy, ileus, dehydration, mild leukocytosis, or hyponatremia. The manifestations of the recurrent attacks should have been similar to each other in nature (although not necessarily in degree or severity). The presence or absence of all such symptoms will be recorded on the CRFs by study personnel who are blinded to the treatment that was given.

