Patients will have laboratory documentation of one of the acute porphyrias. Molecular documentation is also expected, although rarely a causative mutation cannot be detected. Upon entry into the study they will be given in a blinded fashion one or more preventive dose of either PanhematinTM (4 mg/kg) or placebo. The number of infusions will correspond to the number of prophylactic doses of hemin they customarily receive over approximately one week. A recurrent attack within the next 1, 2, 3 and 4 weeks will represent treatment failures. Because at study entry most patients are expected to be on weekly prophylactic hemin treatment, and hemin is a short-acting drug, emphasis in the analysis will be on attacks occurring within 1 week after study treatment.

Any attacks that occur during the study will be treated according to standard of care, which may include Panhematin[™], either at the study site or at the patient's usual treatment location.

It is intended that 20 patients will complete treatment with a single blinded dose and at least 4 weeks of follow up. A completed patient is one who meets all entrance criteria, has no exclusion criteria and completes the single dosing and at least one week of follow up, or is withdrawn because of an adverse event.

The site for this study is the University of Texas Medical Branch (UTMB) at Galveston. The UTMB Porphyria Laboratory will carry out laboratory determinations related to porphyria as needed for this study. DNA studies to identify the familial mutation are now standard of care and will not be done as part of the study.

Porphyria Laboratory and Center Date: June 18, 2019 IND 13,929

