6.2.1.1 Number of attacks and porphyria-related signs and symptoms

At the post-treatment visits the patients will be queried about symptoms attributable to porphyria, treatment that was given for such symptoms and any doctor for hospital visits or admissions since the previous visit. Symptoms recorded will include pain, nausea, vomiting, constipation and specified neurological and psychiatric symptoms. This information will be recorded on the CRFs.

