12.1 Purposes

The main purpose of the statistical analyses is to test the null hypothesis that observed differences between the two treatment groups could have been produced solely by chance – the alternative being that differences were due to the difference in treatment (i.e. Panhematin[™] vs. placebo) – and to estimate the true differences between measurements for the two treatment groups. The emphasis in the efficacy analysis will be the effects of treatment with Panhematin[™] vs. placebo in preventing a subsequent attack in the week following a single infusion. Attacks occurring at weeks 2, 3 and 4 will also be subject to analysis, since recurrent attacks do not always occur at precisely predictable intervals.

Biochemical parameters, such as urine and serum levels of PBG, will be analyzed also, but will not be primary efficacy measures.

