12.2 Variables for statistical analyses

12.2.1 Efficacy variables

The primary efficacy endpoint is the prevention of an acute attack during the first week following a blinded infusion of either Panhematin[™] or placebo, and at other weekly intervals up to one month.

Secondary efficacy and exploratory endpoints include changes in biochemical parameters during treatment, and the effects of genetic, clinical and demographic features on treatment response.

The following biochemical endpoints will be analyzed:

- Urine (or plasma/serum) ALA, PBG
- Urinary total porphyrins, including fractionation of individual porphyrins by HPLC

- Plasma porphyrins, including fractionation of individual porphyrins by HPLC (if elevated initially)
- Fecal porphyrins, including fractionation of individual porphyrins by HPLC (if elevated initially)

Data related to these secondary endpoints will be subjected to descriptive analyses and differences between the treatment groups analyzed for significance as described below.

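### Section 12.3 scores an attack in each separate week, section 3.1 counts any attack up to that week; the two agree for week 1 but can disagree, even in sign, for weeks 2 to 4

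*Combined protocol and SAP*

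**What the plan says.** Two descriptions of the outcome stand side by side in the combined protocol and SAP.

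**Cumulative.**
- Section 3.1: "A recurrent attack within the next 1, 2, 3 and 4 weeks will represent treatment failures".
- Section 2, primary objective: whether hemin "is more effective than placebo in preventing an attack within the next 1-4 weeks".
- Section 3.2 expects the arms to differ over the 4 weeks after dosing.

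**Week by week.**
- Section 12.3 gives the modelled variable as "the occurrence or nonoccurrence of an acute attack each of the 4 weeks following test infusion". The model is a logistic regression with treatment as factor and dose as covariate.
- Section 12.2.1 defines the primary endpoint as prevention in the first week "and at other weekly intervals up to one month".
- Section 12.1: "Attacks occurring at weeks 2, 3 and 4 will also be subject to analysis".

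**Also relevant.**
- Section 3.1 sets the priority: "emphasis in the analysis will be on attacks occurring within 1 week after study treatment".
- Section 4.5 keeps patients in the trial after open-label hemin for an attack, so a patient who fails early still has later weeks to be scored.
- Section 12.4 uses recurrence probabilities of 0.8 and 0.2 without saying what period they cover.

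**The concern.** Take a patient who attacks on day 3, is treated and then stays well. Under section 3.1 that patient is a failure at 1, 2, 3 and 4 weeks. Under section 12.3, read plainly, the patient is a failure in week 1 and a nonoccurrence in weeks 2, 3 and 4. The 12.3 model has no term for an earlier attack, and no rule removes failed patients from the later denominators. The arm with more early attacks therefore has fewer patients left who can have a first attack later, and its failures can be counted as later successes.

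Weeks 2 to 4 are within the primary endpoint of 12.2.1, and section 3.2 admits that the most informative follow-up interval is uncertain. If the scoring is settled after the data are seen, the same 20 patients could support opposite statements about weeks 2 to 4. The recurrence rates that the 10-patient interim analysis feeds into the sample size (12.4) also depend on the scoring if any window beyond week 1 is used.

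**Working it through.** **Inputs from the plan.** Recurrence 0.8 (control) and 0.2 (hemin), 10 per arm, 80% power (12.4); two-sided 5% (12.3). Later weekly risks and repeat attacks are not given, so they are assumptions, varied below. Differences are placebo minus hemin.

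**1. The plan's own figure.** Two-proportion test, pooled variance under the null:

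power = Φ[(d√n − 1.96√(2p̄(1−p̄))) / √(p₁(1−p₁)+p₂(1−p₂))]

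With d = 0.6, n = 10, p̄ = 0.5: (1.897 − 1.386)/0.566 = 0.904, and Φ = 0.817. Exact enumeration of the same test gives 0.805. The stated 80% reproduces. The second example (0.8 vs 0.38) gives 21 per arm, 42 in total against the stated 40.

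**2. A count by hand.** At 0.8 and 0.2, 8 of 10 placebo and 2 of 10 hemin patients fail in week 1. That leaves 2 and 8 attack-free. Suppose half of these attack in week 2 and nobody attacks twice: 1 and 4 new attacks.
- Separate week (12.3): 1/10 vs 4/10, difference -0.30.
- Cumulative (3.1): 9/10 vs 6/10, difference +0.30.

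**3. Constant weekly risk p of 0.8 and 0.2, at most one attack per patient.** Separate week w: p(1−p)^(w−1). Cumulative: 1−(1−p)^w.

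| Week | Separate, placebo vs hemin | Difference | Cumulative, placebo vs hemin | Difference |
|---|---|---|---|---|
| 1 | 0.80 vs 0.20 | 0.60 | 0.80 vs 0.20 | 0.60 |
| 2 | 0.16 vs 0.16 | 0.00 | 0.96 vs 0.36 | 0.60 |
| 3 | 0.03 vs 0.13 | -0.10 | 0.99 vs 0.49 | 0.50 |
| 4 | 0.01 vs 0.10 | -0.10 | 0.998 vs 0.59 | 0.41 |

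At week 2 with 10 per arm, exact enumeration of the two-sided test rejects 2.3% of the time under separate-week scoring and 87% under cumulative scoring.

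**4. As in 3, but failed patients go on attacking at 0.8 and 0.2 per week.** The separate-week difference is 0.60 in every week. The cumulative column is unchanged.

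**5. 0.8 and 0.2 taken as 4-week risks at constant hazard, at most one attack.** Weekly hazards are 1−0.2^(1/4) = 0.331 and 1−0.8^(1/4) = 0.054.
- Separate-week differences: 0.28, 0.17, 0.10, 0.05. Power: 28%, 10%, 3%, 1%.
- Cumulative differences: 0.28, 0.45, 0.55, 0.60. Power at 4 weeks: 80%.

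Week-1 power is 28% under either scoring.

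**6. Hemin patients catch up: 0.8 vs 0.2 in week 1, then 0.8 per week in both arms, at most one attack.**
- Separate-week differences for weeks 2 to 4: -0.48, -0.10, -0.02.
- Cumulative differences for weeks 2 to 4: +0.12, +0.02, +0.005. The difference is diluted but not reversed.

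**The case against.** The strongest answer is that the analysis the plan cares most about is untouched. Sections 3.1, 6.2.1, 12.1 and 12.2.1 all put week 1 first, and week 1 is scored identically both ways. This stands, and it confines the point to weeks 2 to 4.

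Second, a reader might infer that separate-week scoring is biased against hemin in general. The documents do not support that. The reversal needs few repeat attacks, and in step 3 it also needs high constant weekly risks. Section 3.1 expects 6 or more attacks a year before prophylaxis; at that floor the rate is 6/52, about 0.12 per week, so step 3 gives even hemin patients (0.2) more than that. Steps 4 and 5 show no reversal.

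Third, a reader might infer that one attack spanning days 6 to 9 will be counted in two weeks, or that attacks will be assigned by the visit at which they are reported. Neither is stated. In section 2.1, "An acute porphyric attack is defined by the presence of abdominal pain and one or more other characteristic manifestations" is the diagnostic definition, not a weekly scoring rule. The follow-up enquiry in 6.2.1.1, which includes "any doctor for hospital visits or admissions since the previous visit", says what is asked, not how attacks are assigned. Section 6.2.1.2 records times of hemin, glucose and opioid doses, and section 9 requires the duration of signs and symptoms to be verifiable in source. Only an explicit onset-date rule is missing, and that is a minor clarification.

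Finally, the 12.3 phrase lacks a preposition before the word each, so a cumulative reading is not wholly excluded. Sections 12.1 and 12.2.1 nevertheless lean toward separate weeks, and nothing says how weeks after a first attack are scored.

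**Conclusion.** The inconsistency is real and unreconciled for weeks 2 to 4. Sections 2 and 3.1 describe a cumulative outcome; 12.1, 12.2.1 and 12.3 describe a weekly one, with a model that ignores earlier failure. The emphasised week-1 comparison is not affected, so it would be wrong to conclude that the trial's main result is compromised.

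The size depends on assumptions the plan does not settle. With constant weekly risks of 0.8 and 0.2 and at most one attack per patient, the week-2 difference is 0.00 on one scoring and 0.60 on the other, and the separate-week difference then turns to about -0.10. With continued attacks at those risks it stays at 0.60. With 0.8 and 0.2 as 4-week risks it falls from 0.28 to 0.05 but keeps its sign.

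This should be corrected before the interim unblinding. It does not threaten the trial.

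**What to change.** In 12.2.1 and 12.3, align the outcome with section 3.1, for example: *first attack with onset by the end of week 1 (emphasised), and by the end of weeks 2, 3 and 4 (cumulative); a patient who has had an attack remains a failure at later time points. Each attack is counted once, by its onset date.*

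Record the attack onset date on the weekly contact CRF. If separate-week results are wanted, report them descriptively among patients still attack-free at the start of that week. In 12.4, state which window 0.8 and 0.2 refer to.

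The cost is a few sentences and one date field, with no extra visits or patients. There are three downsides. Cumulative time points are correlated with one another. They leave out repeat attacks, which can be listed separately. They can also dilute the difference by week 4 if hemin patients catch up (step 6), which is plausible because section 3.1 calls hemin short-acting. The change does not raise week-1 power if 0.8 and 0.2 turn out to be 4-week risks; that power is 28% under either scoring.

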12.4 Sample size determination

The power to detect a treatment-related difference in frequency of attacks and other measurements increases with the magnitude of the differences that are induced by treatment. A prior case series with cross over from a pre-existing

control period to open label use of heme arginate to prevent frequent attacks showed a substantial effect in some patients, but little effect in others. That study suggests that a sample size of 20 should be sufficient. However, the previous study may not be useful in assessing sample size for the current study, which is of a different design. Therefore, an interim analysis is planned in this study after the first 10 subjects. The biostatistician will unblind the data for this analysis, but blinding will be preserved for all others.

The sample size needed to have 80% power to reject the null hypothesis of no effect using the two-sample comparison of proportions at the 5% significance level will be determined based on the initial sample. For instance, if the probabilities of recurrence are 0.8 and 0.2 in the control and treatment groups respectively, the power to detect with 20 patients (10 patients per group) is 80%. However, if the treatment group chance of recurrence is 0.38, the estimated sample size is 40 (20 patients per group). If the estimated sample size is 20 or less the trial will stop after 20 patients have completed; if it is up to ~40, consideration will be given to increasing the number of completed patients to 40; if it greatly exceeds 40 the trial will continue until 20 patients have been completed. If it is not feasible to reach a target sample size, or if it is not even feasible to find enough patients to have 80% power for establishing clinical efficacy, the trial will continue and stop when 20 patients have completed.

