12.5 Interim analyses

An interim analysis is planned after completion of 10 subjects, to determine a reasonable estimate of the variance, as stated above in 12.4. Given the change in inclusion criteria, a logistic model will be fit to assess the change in recurrence rate by dose. We do not, however, expect that the dose or regimen effect will be statistically significant or have a substantial effect on the outcome.

13. Ethical considerations

The study will be conducted in accordance with accepted standards for human studies, including the Declaration of Helsinki. The study will be approved by the IRB at UTMB, as will changes made in study documents as appropriate.

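### Section 12.3 plans ordinary logistic regression with no named test and no rule for an arm with 0% or 100% attacks; at 10 per arm and 0.8 vs 0.2 power is 60% to 82%, depending on that choice

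*Combined protocol and SAP*

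**What the plan says.** Section 12.3 states that attack or no attack in each of the four weeks after the infusion "will be analyzed by logistic regression with treatment as a factor and drug dose as a covariate". Tests are to be "two sided at the 5% significance level and accordingly 95% confidence intervals will be determined". The section does not say whether treatment is tested by a Wald, likelihood-ratio, score, exact or penalised method. Exact methods (Wilcoxon, Fisher) are named there only for use of Panhematin and opioids.

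Section 12.4 bases its power on a different procedure, "using the two-sample comparison of proportions at the 5% significance level". For attack rates of 0.8 and 0.2 it states that "the power to detect with 20 patients (10 patients per group) is 80" per cent. It adds a second example of 20 per group for 0.8 vs 0.38. On the interim analysis after 10 subjects it says: "The biostatistician will unblind the data for this analysis, but blinding will be preserved for all others".

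The documents do not define drug dose. Section 3.1 lets the number of blinded infusions follow each patient's usual regimen. Section 5.1 sets 4 mg/kg with a cap of 313 mg. Section 5.2 gives placebo patients saline. Section 12.5 adds only that the authors do not "expect that the dose or regimen effect will be statistically significant or have a substantial effect on the outcome".

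**The concern.** With 10 patients per arm and a strong effect, an arm with 0/10 or 10/10 attacks is an ordinary outcome. The maximum-likelihood odds ratio is then infinite (separation), and standard software prints a huge standard error with a Wald p-value close to 1. The trials affected are those with the clearest treatment difference.

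An analyst who meets this must improvise, and the usual repairs differ in power and in type I error. The biostatistician sees unblinded data after 10 patients, so the repair should be fixed in advance.

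The covariate adds a second open choice. If drug dose meant hemin received, with zero for placebo, it would nearly duplicate the treatment factor.

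**Working it through.** **Inputs.** Two-sided 5% (12.3). 10 per arm at 0.8 vs 0.2, and 20 per arm at 0.8 vs 0.38 (12.4). 1:1 allocation (5.7). One binary outcome per patient, for example attack in week 1; fixed sample size; treatment-only model, because the covariate is undefined.

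**1. The plan's own figure.** The pooled two-proportion formula is power = Φ{[d√n − 1.96√(2p̄q̄)] / √(p₁q₁ + p₂q₂)}. With d = 0.6, n = 10 and p̄ = 0.5 this is Φ{[1.897 − 1.386] / 0.566} = Φ(0.904) = 81.7%. Exact enumeration of all 11 × 11 outcomes with the uncorrected chi-square test gives 80.5%. The stated 80% is right for a comparison of proportions.

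**2. How often separation occurs.** An arm at rate 0.8 (or 0.2) is at 0/10 or 10/10 with probability 0.8¹⁰ + 0.2¹⁰ = 0.1074. At least one arm: 1 − (1 − 0.1074)² = 20.3%.

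**3. Power and type I error by test.** The Wald statistic is z = ln[a(n−b) / (b(n−a))] / √[1/a + 1/(n−a) + 1/b + 1/(n−b)], where a and b are the attack counts. It does not exist when a or b is 0 or n, and such tables count as non-significant. Maximum size is the largest type I error over common attack rates from 0.001 to 0.999.

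| Test, 10 per arm | Power, 0.8 vs 0.2 | Maximum size |
|---|---|---|
| Wald | 60.2% | 3.9% |
| Pearson (= score) | 80.5% | 4.2% |
| Firth penalised likelihood ratio | 80.5% | 4.2% |
| Ordinary likelihood ratio | 82.0% | 8.8% |

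Pearson and Firth reject the same tables at 10 per arm. The gap to Wald, 80.5 − 60.2 = 20.3 points, consists entirely of separated tables. The likelihood-ratio size is 8.7% at a common rate of 0.2, 7.7% at 0.3 and 5.2% at 0.5.

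**4. One separated table.** Take 8/10 attacks on placebo and 0/10 on hemin. Ordinary logistic regression gives a Wald p of about 0.999 and no finite Wald interval. The Firth odds ratio is (8.5/2.5) / (0.5/10.5) = 71, with 95% CI 5.8 to 10,510 and p = 0.0002.

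**5. Larger effects (assumed; not in the documents).** At 0.8 vs 0.1, separation occurs in 41.9% of trials, and power is 51.8% for Wald against 93.7% for Firth. At 0.8 vs 0.05 the figures are 64.2%, 33.5% and 97.6%.

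**6. 20 per arm, 0.8 vs 0.38.** Separation occurs in 1.2% of trials. Power is Wald 75.8%, Firth 77.0% (maximum size 5.0%) and Pearson 79.1% (maximum size 5.3%).

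**7. With a covariate.** This was simulated with the number of infusions as covariate, 5,000 trials per setting, 10 per arm, 0.8 vs 0.2. It was assumed that 50% to 90% of patients have one infusion, that the rest have 2 to 4, and that the covariate has no effect. Power is Wald 54–56%, likelihood ratio 82–83% (size up to 9.9%) and Firth 79–80% (size up to 5.2%). The pattern is the same.

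**The case against.** The plan never mentions Wald. Score and likelihood-ratio tests are also logistic regression, and in a treatment-only model the score test is the very comparison of proportions that 12.4 uses. A reader might infer that the trial really has 60% power, or that the 80% in 12.4 is wrong. The documents support neither. The 80% is reproduced, and 60.2% needs two added assumptions: that Wald is used, and that every separated table is reported as non-significant. It is the low end of a range.

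A reader might also infer that power falls as hemin works better. That holds for Wald only, and the rates that show it (0.1 and 0.05) are illustrations, not planning values.

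The exact figures are for one binary outcome without a covariate, whereas 12.3 has a covariate and four weekly outcomes. The covariate results rest on an assumed spread of regimens. Drug dose could also mean milligrams: under the 5.1 cap, milligrams stop rising above 313/4 ≈ 78 kg, and placebo patients have no evident value. The sponsor's intended meaning cannot be settled from the text.

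The 77.0% at 20 per arm follows from choosing Firth. It is not an error in 12.4, where the proportions test gives 79.1%. Which week is primary is a separate question and is not decided here.

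What remains is that the text permits methods that differ by about 20 points of power or double the type I error, and that ordinary logistic regression cannot deliver the promised finite interval in about one trial in five.

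**Conclusion.** The point holds as a gap in the specification with a conditional but sizeable consequence. At 10 per arm and 0.8 vs 0.2, the unnamed test leaves power anywhere from 60.2% to 82.0%, and maximum type I error from 3.9% to 8.8%. In 20.3% of trials the odds ratio is infinite and has no finite Wald interval. Firth or score tests deliver the 80% in 12.4 within the 5% level. At 20 per arm with 0.8 vs 0.38 little is lost.

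These figures assume a treatment-only model, one binary outcome per patient and a fixed sample size. The matter is worth fixing because 20 patients is both the default and the fallback size in 12.4. Logistic regression itself is not at fault.

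**What to change.** In 12.3, replace ordinary logistic regression with: *Firth penalised-likelihood logistic regression, two-sided penalised likelihood-ratio test at 5%, odds ratio with profile penalised-likelihood 95% CI.* This handles separation without a further rule. Fix it before any further unblinded look; the documents do not show whether the interim analysis has taken place. If it has, the amendment should say so and state who had seen unblinded data.

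Define the covariate as a quantity that exists in both arms and is set before randomisation, such as the number of scheduled blinded infusions. It should not be hemin received, which is nearly aliased with treatment. Otherwise, move the covariate to a supportive model.

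In 12.4, state that the 80% at 10 per arm holds for this test (80.5%, unadjusted, fixed sample size), and that its power at 20 per arm with 0.8 vs 0.38 is 77.0%.

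The cost is an amendment to the statistical section, with IRB approval (13.4) and submission to FDA (13.5). No new data or procedures are needed. Intervals in separated tables will be very wide, as the 5.8 to 10,510 example shows, and the 40-patient example will show power somewhat below 80%.
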